Study Protocol

A proof-of-technology, pilot, single-site, open-label, prospective clinical study to investigate the feasibility and performance of PROVIZ – a radiomics-based machine learning software, to support targeting of prostate biopsies on magnetic resonance images in biopsy-naive patients.

This document represents a direct extraction of pertinent sections from the approved Clinical Investigation Plan (CIP) Version 1.5, dated 22nd January 2024, tailored to outline the study protocol.

1.1.1 List of abbreviations:

Abbreviation	Term
ADC	Apparent diffusion coefficient maps
ADE	Adverse device effect
AE	Adverse event
AI	Artificial intelligence
ASADE	Anticipated serious adverse device effect
AUC	Area under the receiver operating characteristic curve
bpMRI	bi-parametric MRI
CAD	Computer-aided detection and diagnosis
CIP	Clinical investigation plan
CRF	Case report form
csPCA	Clinically significant prostate cancer
DD	Device deficiency
DRE	Digital rectal examination
DWI	Diffusion-weighted imaging
eCRF	Electronic Case report form
EU	European union
FROC	Free-response receiver operating characteristic curve
GUI	Graphical user interface
Hemit	Central Norway regional health IT
IB	Investigator's brochure
ICD	Informed consent document
ID	Identity document
ISO	International organization for standardization
mpMRI	multi-parametric MRI
MRI	Magnetic resonance imaging
NTNU	Norwegian university of science and technology
PACS	Picture archiving and communication system
PI	Principal investigator
PI-RADS	Prostate imaging-reporting and data system
PSA	Prostate-specific antigen
REC	Regional committee for medical and healthcare research ethics
SADE	Serious adverse device effect
SAE	Serious adverse event
SaMD	Software as a medical device
SIL	Subject identification log
SLV	The Norwegian medicines agency
SOP	Standard operating procedure
T2W	T2-weighted imaging
UADE	Unanticipated adverse device effect
USADE	Unanticipated serious Adverse device effect

6.4 Procedures

6.4.1 Clinical investigation procedure

The clinical investigation procedure is summarized in Figure 6.4.1 and the decision to send patients for biopsy sampling summarized in Figure 6.4.2.

[figure not shown]

Figure 6.4.1: Summary of the clinical investigation workflow.

[figure not shown]

Figure 6.4.2: Simplified explanation on how lesions are selected for biopsy during the prospective study.

The patient meets for an invited MRI scan due to a suspected prostate cancer according to current clinical practice. A research coordinator checks to see if the patient meets the inclusion criteria for the investigation. This is done by asking the patient and checking the patient records. If the patient meets the criteria, then he is eligible for enrollment. He is then given an informed consent to participate that explains the purpose of the study, the risks and benefits, and the participant's rights in layman's terms. Oral and written information will be given to the patient prior to scanning, and any questions will be answered. Patients accepting to take part will sign the informed consent after the scanning.

The clinical investigation step by step as follows:

1. Patient scanned using MRI with bpMRI protocol.
2. The patient scan is stored in the production PACS (i.e., the hospital PACS) system.
3. The images will be deidentified and the patient will get a pseudonym, before they sent to the local PACS (i.e., the study server PACS). All the sensitive, identifiable, and locatable information by means of a standard identification mechanism within the metadata for the patients and the physicians will be anonymized.

[figure not shown]
4. A password-protected Subject Identification Log (SIL) linking subject names to newly assigned IDs will be created and updated for each newly enrolled subject. The spreadsheet is stored in the hospital system and the password is only accessible to authorized individuals.
5. The images will be sent to the local PACS on the sever via teleradiology.
6. The radiologist will open the patient scan using the production PACS, as usual, check the images, and identify the suspicious areas, which need to be biopsied, according to PI-RADS.
7. The radiologist will open the GUI desktop application from his/her workstation and check the software outputs (i.e., tumor probability map, the detection map, and gland segmentation). Here the pseudonym will be used from the SIL to enquire the subject in the local PACS.
8. The radiologist compares his/her findings with the results of the investigational software. If there are areas detected by the software (detection map) that were not detected by the radiologist, the radiologist selects these areas (up to 3 areas).
9. The radiologist will fill a report in the eCRF to be used by researchers only, flagging the detected areas for biopsy sampling into:
 - a. Defined solely by the radiologist, with PI-RADS score + location.
 - b. Overlap between the radiologist and the investigational software, with PI-RADS score + location.
 - c. Defined solely by the investigational software, with location.

The location should be according to the areas identified by PI-RADS (Figure 6.4.3).

Table 6.4.1 gives an example on the report.

Table 6.4.1: Example of radiological report of findings, for research purposes only.

Pseudonym		POT0001		
Finding number	Human	Investigational software	Finding Location	PI-RADS score
1	x		Mid-PZpm-R	3
2	x		Apex-PZa-L	4
3	x	x	Base-PZpl-R	4
4		x	Mid-PZa-L	N/A

**Figure 6.4.3:** The prostate regions according to PI-RADS.

10. The radiologist fills out the report as usual without identifying whether a finding is identified by the investigational software or human, keeping the lesion number. The radiologist will add a sentence to his report indicating that some of these lesions may have been identified by investigational software.

11. The radiologist then opens Eigen Artemis Profuse software (Eigen Health, CL, USA) to delineate the prostate and suspicious lesions as usual. The radiologist semi-automatically delineates and adjusts the entire prostate after reviewing the automatic segmentation on the GUI screen. This is followed by delineation of the suspicious findings by the radiologist and the AI (up to 3 solely AI findings). Note that radiologists begin delineation in order (i.e., lesion 1, then 2, then 3, then 4, as indicated in the report in order).
12. The radiologist will export the delineations file to the Eigen ARTEMIS - Prostate Fusion Biopsy System (Eigen Health, CL, USA).
13. The urologist will review the radiologist's report and unless the patient has contraindications to prostate biopsy (due to comorbidity or remaining life expectancy) the patient will be registered for biopsy sampling procedure.
14. When the patient arrives for the biopsy, he is prepared as usual.
15. Prior to biopsy, the operating room nurse will import the radiologist's segmentations into the Eigen ARTEMIS - Prostate Fusion Biopsy System (Eigen Health, CL, USA).
16. The urologist will perform an ultrasound scan for fusion with the MRI scan.
17. The urologist will then obtain biopsies according to the standard clinical procedure. This includes targeting the delineated suspicious areas at least once. In some cases, the urologist may perform a systematic biopsy in addition to the targeted biopsy. The urologist will ask the nurse to place each biopsied specimen in a plastic tube immediately after collection and to immediately label the tube with Lesion 1, 2, 3 ... etc. (corresponding to the lesion number assigned by the radiologist for the targeted biopsies) in addition to labelling the biopsy location according to PI-RADS (Figure 6.4.3).
18. The tubes are sent to pathology department for histopathological evaluation. Each lesion is evaluated separately. Some suspicious areas may have more than one biopsy taken from them. Then they are pooled and evaluated together to determine the overall Gleason score for each lesion separately.
19. The data will be collected by the researchers, once every week, where the patient pseudonym (e.g., POT0001) will be used to name folders and deidentify scans upon exporting. The subject's scan images are pseudonymized and exported to an encrypted external hard drive and then uploaded to the lab at HUNT cloud. The graphical report of the biopsy procedure might be exported from the ARTEMIS

system to an encrypted external hard drive and then uploaded to the laboratory at HUNT cloud. The radiologist's report on the patient is exported to the Digital Life lab at HUNT cloud. The patient's clinical information is collected and exported to the lab at HUNT cloud. The lesion-based histopathology assessment report is exported to the lab at HUNT cloud.

20. The data collected will finally be used for analyses according to primary and secondary objectives of the study.

Overall, the deviation from normal clinical practice is very small. Deviations mainly relate to subject enrollment, the inclusion of test software in image analysis, and the storage and export of data for research. Specifically, the deviation is in steps 3, 5, 7, 8, 9, 19, and 20.

Steps 3, 4, and 5 will be performed by HEMIT; steps 7, 8, and 9 will be performed by the radiologist; and steps 4, 19, and 20 will be performed by the sponsor's representatives (research coordinators), see Section 6.4.2.

Additional activities to the above procedure include user reporting of safety-related concerns or adverse events, or software-related bugs or errors to the PI and communication between the clinic and the PI to determine if it is necessary to suspend or terminate the study early. In addition, software users will be trained in the proper use of the software prior to the start of the investigation.

14. 5 Procedures for recording and reporting Adverse Events and Device Deficiencies

All adverse events, effects, device deficiencies, and related information will be recorded in detail in the medical records and the eCRF by the investigator or one of his/her delegate. The investigator will report all of these to the sponsor as it is specified in Table 14.4.1. The Sponsor will report all reportable events to the SLV in accordance with the SLV reporting procedure within the timeframes specified in Section 14.4.

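### Does capping software-only areas at three, with no software output named in the export list, lose the count of what the software found?

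*Protocol*

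**What the plan says.** The title states that the study is meant "to investigate the feasibility and performance of PROVIZ". In section 6.4.1, step 7, the radiologist opens the desktop application to "check the software outputs (i.e., tumor probability map, the detection map, and gland segmentation"). Step 8 then adds software areas that were "not detected by the radiologist, the radiologist selects these areas (up to 3 areas"). Step 9 is a research-only eCRF report, completed by "flagging the detected areas for biopsy sampling into" three categories. The last of these is "Defined solely by the investigational software, with location". Step 11 repeats the limit, describing "delineation of the suspicious findings by the radiologist and the AI (up to 3 solely AI findings").

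Step 19 describes the weekly collection: scan images, the radiologist's report, clinical information, lesion-level histopathology and, less firmly, a biopsy record ("The graphical report of the biopsy procedure might be exported from the ARTEMIS" system). Step 20 says the collected data serve the primary and secondary objectives. Those objectives are not part of this extract. Figure 6.4.2, captioned "Simplified explanation on how lesions are selected for biopsy during the prospective study", is not reproduced.

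**The concern.** In a study of a detection tool, the number of extra areas the tool produces per patient is a natural descriptive quantity, and so is how often that number exceeds what the clinic agreed to sample. Here the report is filled in after the cap has been applied, and it has no described place for a software-only area that was found but not taken. The detection map would show the full number, but step 19 does not name it.

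A count taken from category c alone would then be cut off at three. A yield computed from it would describe the areas that were sampled, not everything the software marked. A field that is not captured at source cannot be supplied later by an analysis plan, so the matter is worth checking while the study is running.

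**Working it through.** The protocol gives no figure for software-only areas per patient, so there is nothing of its own to reproduce. Its one illustrative patient (Table 6.4.1) has a single software-only finding.

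**1. The recording rule.** Let k be the number of software-only areas in a patient. If every such area is taken until the cap is reached (the plainest reading of step 8), the recorded number is min(k, 3):

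| k | 0 | 1 | 2 | 3 | 4 | 5 | 6 | 7 |
|---|---|---|---|---|---|---|---|---|
| recorded | 0 | 1 | 2 | 3 | 3 | 3 | 3 | 3 |

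Three and more than three do coincide. If the radiologist may decline areas, records of one or two are ambiguous as well, and min(k, 3) no longer describes the data.

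**2. Scale, under assumed means.** The share over the cap is P(k>3). The share of three-row records that hide more is P(k>3)/P(k≥3). The mean recorded count is P(k≥1)+P(k≥2)+P(k≥3).

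Poisson:

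| Assumed mean | P(k>3) | P(k≥3) | Ratio | Mean recorded |
|---|---|---|---|---|
| 0.5 | 0.0018 | 0.0144 | 0.122 | 0.498 |
| 1 | 0.0190 | 0.0803 | 0.236 | 0.977 |
| 2 | 0.1429 | 0.3233 | 0.442 | 1.782 |
| 3 | 0.3528 | 0.5768 | 0.612 | 2.328 |

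Negative binomial with variance twice the mean (p = 0.5, r = mean):

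| Assumed mean | P(k>3) | Ratio | Mean recorded |
|---|---|---|---|
| 0.5 | 0.0222 | 0.446 | 0.459 |
| 1 | 0.0625 | 0.500 | 0.875 |
| 2 | 0.1875 | 0.600 | 1.563 |
| 3 | 0.3438 | 0.688 | 2.063 |

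The check at mean 1 is short: P(k>3) = 0.5⁴ = 0.0625, P(k≥3) = 0.5³ = 0.125, ratio 0.5, and 0.5 + 0.25 + 0.125 = 0.875.

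**3. Is step 19 a complete inventory?** Set it beside steps 9 and 10. The source labels (radiologist, both, software) sit in the step 9 eCRF report. The ordinary report of step 10 deliberately conceals the source of each finding. Step 19 mentions only the radiologist's report on the patient and does not separately name the eCRF form. If the list were closed and read strictly, it might not carry the source labels either, although the form exists for the researchers. The list is therefore a description of the weekly collection, and its silence on the detection map does not show that the map is discarded. Steps 3, 5 and 7 place the images on a study server, where they are looked up by pseudonym. Whether outputs are kept there is not stated either way.

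**4. Can the count be recovered?** Step 19 exports the scans. Running the same software version on them gives the total number of detections, d. The report gives the number of category b rows, b. If overlapping findings match one to one, k = d − b, with no cap.

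**The case for a change.** The best case for acting is that the literal reading is right, the quantity fits the stated purpose, and the cost looks small. No step says the software will be run again. A re-run would not explain why an area was left out, and it does not by itself prove that its output is what the radiologist saw. Even where exceedance is rare, a record of three is ambiguous.

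The ambiguity in the listed data stands, and so does the fact that the reason for omission cannot be rebuilt. Neither carries far. No objective or endpoint shown uses the count or the reason, and no stated result would be wrong. Areas beyond the cap have no histology whatever is recorded, so a fuller count would not say whether they are false positives.

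The obvious additions are also weaker than they look. The delineations file of step 12 follows step 11 and is limited to three software-only findings, so it cannot separate three from more. A line giving the place of each omitted area and the reason would oblige the radiologist to enumerate and locate every remaining detection, which is more than a single extra entry.

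**Conclusion.** The observation is accurate as a reading of steps 8, 9, 11 and 19, but it does not call for a change. It is missing detail in an extract of the Clinical Investigation Plan, and a data manager or analyst would resolve it by keeping the software output or by running the software again on the exported scans.

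The size is unknown. Under assumed means of 0.5 to 3, patients over the cap range from 0.2% to 35.3% (Poisson) or 2.2% to 34.4% (negative binomial). Those figures describe ambiguity in one descriptive count, not bias in a result, and the recorded means hold only if every software-only area is taken up to three.

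The conclusion rests on two assumptions: the software version used in the study remains available, and no objective outside this extract depends on the uncapped count with no other source for it. If either failed, the point would deserve another look.

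### The radiologist's own findings and PI-RADS scores are first stated to be recorded after the software maps have been seen, with no locked unaided list to check them against

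*Protocol*

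**What the plan says.** All steps are in Protocol section 6.4.1.

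- **Step 6.** In the production PACS, the radiologist is to "check the images, and identify the suspicious areas, which need to be biopsied, according to PI-RADS". No entry, save or lock is mentioned.
- **Step 7.** "The radiologist will open the GUI desktop application from his/her workstation and check the software outputs", that is, the probability map, the detection map and the gland segmentation.
- **Step 8.** "The radiologist compares his/her findings with the results of the investigational software". Software-only areas are defined as "areas detected by the software (detection map) that were not detected by the radiologist", and up to three of them are selected.
- **Step 9.** "The radiologist will fill a report in the eCRF to be used by researchers only, flagging the detected areas for biopsy sampling into" three groups: (a) radiologist only, (b) "Overlap between the radiologist and the investigational software, with PI-RADS score + location", and (c) software only, with location.
- **Table 6.4.1**, captioned "Example of radiological report of findings, for research purposes only", has one PI-RADS score column per finding, with N/A for the software-only finding. It has no field separating entries made before and after the software was viewed.
- **Step 10.** The clinical report is written after the eCRF report and does not show which source a lesion came from.

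**The concern.** Overlap and software-only labels can only be assigned once the maps have been seen, so doing this at step 9 is not the fault. The fault is that the list they are judged against is not stated to be fixed beforehand. By the step 8 definition, the split between (b) and (c) depends on what the radiologist had detected before opening the maps. Under the visible procedure, that is whatever the radiologist reports at step 9, after seeing them. A borderline area that the software also marks can be remembered as already seen. A weak finding that the software does not mark can be left out. A PI-RADS score can move, and in the layout of Table 6.4.1 the revision would not show.

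The title describes a "prospective clinical study to investigate the feasibility and performance of PROVIZ". Categories a, b and c are where the visible procedure credits each flagged lesion to the radiologist, the software or both. Two uses of the data are exposed: any count of what the software added, and any use of the PI-RADS score as an unaided score. If that reader's pre-software list is not captured, no later analysis can recover it.

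**Working it through.** The plan states no figure on this point, so there is none to reproduce. The check has three parts.

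**1. Search for a pre-software record.** Step 6 states none. Steps 7 and 8 expose the radiologist to the maps. The eCRF report (step 9), clinical report (step 10) and delineation (step 11) all come afterwards, and the clinical report hides the source. The closing text of section 6.4.1 lists the departures from normal practice as steps 3, 5, 7, 8, 9, 19 and 20. Step 6 is not among them, so nothing indicates a research entry there. The exports named in step 19 include no pre-software read.

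**2. The plan's own example.** Table 6.4.1 has findings 1 and 2 as radiologist-only, 3 as overlap and 4 as software-only, so a/b/c = 2/1/1.

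- If finding 4 is entered as overlap, the split is 2/2/0 and the software's only added finding disappears.
- If finding 1 (PI-RADS 3, not marked by the software) is left out, the split is 1/1/1 and the radiologist's total falls from 3 to 2.

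The two changes act differently, so the direction of error cannot be set in advance.

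**3. Illustration of size. All inputs are assumed.** Per 100 lesions marked by at least one reader, let B be both, R radiologist only and S software only, with R = S so that the true difference in detection share is 0. Error rates are 10%, 20% and one third. Differences are radiologist minus software, in percentage points.

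- **A. A fraction f of S is entered as overlap.** The denominator stays 100. Radiologist = B + R + Sf and software = B + S, so the difference is Sf. The software-only count becomes S(1 − f).
- **B. A fraction g of R is not entered.** n = 100 − Rg. Difference = −100·Rg/n.
- **C. Both, with f = g.** n = 100 − Rf. The difference stays 0 because R = S. Overlap share = (B + Sf)/n.

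| B/R/S | A: difference at 10%, 20%, 1/3 | B: difference at 10%, 20%, 1/3 | C: overlap share at 10%, 20%, 1/3 |
|---|---|---|---|
| 80/10/10 | +1.0, +2.0, +3.3 | −1.0, −2.0, −3.4 | 81.8%, 83.7%, 86.2% |
| 70/15/15 | +1.5, +3.0, +5.0 | −1.5, −3.1, −5.3 | 72.6%, 75.3%, 78.9% |
| 60/20/20 | +2.0, +4.0, +6.7 | −2.0, −4.2, −7.1 | 63.3%, 66.7%, 71.4% |

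Worked case, 70/15/15 at one third: A gives 15 × 1/3 = +5.0, and the software-only count falls from 15 to 10. B gives −5/95 = −5.3. C gives 75/95 = 78.9%, against a true overlap of 70%.

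In A the software-only count falls by exactly the error rate in every split. PI-RADS revision is not sized, because the document gives no score distribution.

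**The case against.** The strongest reply is that this is silence in an extract. The document presents itself as selected sections of a larger Clinical Investigation Plan. Figures 6.4.1 and 6.4.2, section 6.4.2, the objectives and the eCRF specification are not visible, and a two-stage entry could sit in any of them. Table 6.4.1 is only an example. The stated order is also protective: the unaided read comes first, step 8 presupposes findings already made, category (a) keeps radiologist-only findings, software-only areas carry no PI-RADS score, and no step tells the reader to drop, relabel or rescore anything.

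Much of this stands. It limits the point to the visible procedure and means that contamination is possible, not shown. It does not remove the point. A reader who follows the stated steps exactly still makes the first stated record after exposure, and nothing visible exists to check it against.

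Two further limits also stand. Moving an area from (c) to (b) leaves the software's own set, b + c, unchanged and removes no lesion from biopsy, so stand-alone software performance on targeted lesions is not affected by that shift. And because step 19 exports the pseudonymised scans, a separate software-blind read could later supply an unaided reference. It would not restore the original reader's list, and it would need the extra reading that a locked entry avoids.

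The illustration rests wholly on assumed splits and rates, and the zero difference in C follows from setting R = S and f = g. It does not set the weight of the point.

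**Conclusion.** The concern holds. In the visible procedure the radiologist's findings, locations and PI-RADS scores are first stated to be recorded after the software maps have been opened and compared, with no prior record or lock. The consequence is confined to attribution between radiologist and software, counts of what the software adds, and use of PI-RADS as an unaided score.

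The direction is unknown and the documents allow no estimate of size. Under the assumed inputs, the radiologist-minus-software difference runs from −7.1 to +6.7 points when the truth is 0, and the software-only count falls by up to a third. The weight for a particular endpoint is unknown because the objectives are not in the extract. The point should be fixed, because the lost information cannot be recovered and the remedy is cheap. Confidence is medium, since a lock may exist in text that is not visible.

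**What to change.** Insert a step between 6 and 7: the radiologist enters the location and PI-RADS score of each own finding in the eCRF, and the entry is time-stamped and locked before the software is opened. After step 8, add the software-only areas, log any later change to a finding or score in separate after-software fields, and assign categories a, b and c against the locked list. If the eCRF already works this way, say so in steps 6 to 9.

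The cost is one more entry step per patient, the additional fields with a change log, and an amendment to the eCRF and the Clinical Investigation Plan. The essential part is the dated, locked entry before step 7. No extra reader, scan or biopsy is needed, and the change sets no rule on which areas are biopsied.

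### Do optional systematic cores, whose histology is not named in any export, undermine the performance data?

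*Protocol*

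**What the plan says.** All of this is in the Protocol, section 6.4.1.

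- **Biopsy (step 17).** "The urologist will then obtain biopsies according to the standard clinical procedure. This includes targeting the delineated suspicious areas at least once". Systematic sampling is optional: "In some cases, the urologist may perform a systematic biopsy in addition to the targeted biopsy". The extract gives no criterion for it and does not ask for a reason.
- **Labelling (step 17).** Each specimen goes into its own tube with a lesion number, described as "corresponding to the lesion number assigned by the radiologist for the targeted biopsies", and with its PI-RADS location.
- **Pathology (step 18).** The tubes go to pathology. Each lesion is read separately, and several cores from one lesion are pooled into one Gleason score. Systematic cores are not mentioned.
- **Export (step 19).** "The lesion-based histopathology assessment report is exported to the lab at HUNT cloud". Scans, the radiologist's report and the patient's clinical information are also exported. The ARTEMIS item is softer: "The graphical report of the biopsy procedure might be exported from the ARTEMIS" system.
- **Software-only areas (step 8).** Where the software marks something the radiologist did not, "the radiologist selects these areas (up to 3 areas").

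The title gives the aim as to "investigate the feasibility and performance of PROVIZ". The opening statement says that the document is an extraction of sections from the Clinical Investigation Plan (CIP).

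**The concern.** Systematic cores are the only tissue the document describes from outside the areas marked by the radiologist or selected from the software. They are therefore the only described source of information on cancers that both missed. A systematic core has a PI-RADS sector on its tube but no radiologist-assigned lesion number. Read strictly, a lesion-based pathology report need not contain it, and the ARTEMIS report that might show it need not be exported.

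If such results reached the research data for some patients and not others, nobody could count the cancers outside all marked areas, or the patients in whom they had been looked for. An absolute sensitivity computed from such data would have too small a denominator and so be too high. Because systematic cores are taken selectively, and the extract asks for no reason, the analyst could not judge how selective the verification was.

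**Working it through.** **Tracing the data.** The plan states no sample size, rate or sensitivity on this point, so there is no figure of its own to reproduce. The check is to follow a systematic core from tube to research data.

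| Route | Certain? | Stated to carry systematic-core histology? |
|---|---|---|
| Lesion-based histopathology report (step 19) | Yes | Not said |
| Clinical information (step 19) | Yes | Content not listed |
| ARTEMIS graphical report (step 19) | No | Content not listed |
| eCRF report of findings (step 9, Table 6.4.1) | Yes | No; holds radiologist and software findings |

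No route meets both conditions, so the observation is correct as a reading of the text. Nor is any route closed. The labelling sentence covers each biopsied specimen, the tubes go to pathology without exception, and two unconditional exports could contain the result. The text is silent; it does not exclude the cores.

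A core targeted at a numbered lesion has its lesion number, its sector, its Gleason score and a certain export. Comparisons between the three finding types in step 9 (radiologist only, both, software only) use these data alone.

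**Illustrative size.** Every input here is assumed; none comes from the document. Take 100 clinically significant cancers, of which the radiologist finds 75. Let m be the number outside all marked areas (5 to 20), s the share of patients given systematic cores (0.3 to 0.6), and e the chance that such cores find a cancer that is there (0.5 to 0.7). Every patient is taken to be biopsied, and targeted cores to miss nothing.

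- Cancers found by systematic cores = m × s × e. Smallest: 5 × 0.3 × 0.5 = 0.75. Largest: 20 × 0.6 × 0.7 = 8.4.
- Apparent sensitivity if none of these results is exported = 75 / (100 − m).
- Apparent sensitivity if all are exported = 75 / (100 − m + m × s × e).

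| m, s, e | None exported | All exported | Removed by export (points) | Left over 75% (points) |
|---|---|---|---|---|
| 5, 0.3, 0.5 | 75/95 = 78.9% | 75/95.75 = 78.3% | 0.6 | 3.3 |
| 5, 0.6, 0.7 | 75/95 = 78.9% | 75/97.1 = 77.2% | 1.7 | 2.2 |
| 15, 0.3, 0.5 | 75/85 = 88.2% | 75/87.25 = 86.0% | 2.3 | 11.0 |
| 20, 0.3, 0.5 | 75/80 = 93.8% | 75/83 = 90.4% | 3.4 | 15.4 |
| 20, 0.6, 0.7 | 75/80 = 93.8% | 75/88.4 = 84.8% | 8.9 | 9.8 |

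Differences are taken before rounding.

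The share of the excess that full export removes is 100 × s × e / (100 − m + m × s × e). It rises with m and with s × e, so its maximum over these ranges is at m = 20, s = 0.6, e = 0.7: 42 / 88.4 = 47.5%. In the third row it is 15 / 87.25 = 17.2%. The larger part of the bias always remains, because most cancers outside the marked areas are never sampled or are missed by the cores.

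**The case for a change.** The strongest case for a change is that data collection belongs in the protocol, and step 19 settles it in writing. Making the ARTEMIS export optional is a stated choice that permits variation between patients, not a detail deferred to an analysis plan. The results arise in routine care, so a sentence in step 19 and one eCRF item would secure them without any extra procedure for the patient. Reasons for systematic sampling that were never recorded may be hard to recover later.

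Some of this stands. The wording is loose, and naming systematic-core histology in step 19, with a yes/no item for whether such cores were taken, would do no harm.

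It does not establish that anything is fixed wrongly. That no reason is recorded is known only for this extract; the full eCRF and the rest of the CIP are not shown. The ARTEMIS export is a second source that matters little if pathology results are collected in full. Asking for a reason would also put a research task on the urologist. Section 6.4.1 does not list step 17 among the departures from normal practice, and it assigns the urologist none of the research steps it allocates.

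**Conclusion.** The concern is accurate about the wording but does not call for a change. It is missing detail in an extract, of a kind that a study team collecting pathology results each week would ordinarily fill by taking the histology of every labelled tube. No rule in the text is shown to produce a wrong result.

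The harm depends on an endpoint that is not shown, such as absolute sensitivity or a count of cancers missed by both. For a proof-of-technology pilot of software that supports targeting, the histology of targeted areas is secure, and yield by finding type does not depend on systematic cores.

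The 0.6 to 8.9 points are illustrative only. They rest on four assumed inputs and compare total loss with total capture, so they are a ceiling for partial loss under those inputs. They describe the radiologist's sensitivity rather than the software's. For the full software output even the direction is not assured, because software-only areas are chosen by the radiologist and limited to three. At best, export would remove just under half of the excess; the rest comes from systematic sampling being optional and imperfect, which better records cannot alter.

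The conclusion assumes that the CIP and eCRF not shown do not exclude systematic-core results from collection. Nothing in the extract suggests that they do.
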